3.4 EXPOSURE TO IMP AND OCS

3.4.1 Available data

For each IMP administration and OCS administration, the start and end date, doses (per administration), dose units and the volume with units (for IMP only) will be recorded.

	Statistical Analysis Plan	
ARGX-113-2010	Final analysis	Final 1.0 of 29APR2025

3.4.2 *Derivation rules*

The total number of IMP administrations in the study will be derived as the sum of all administrations of IMP.

OCS is defined in section 3.3.2. OCS dose (mg) and OCS dose per body weight (mg/kg) will be calculated for each day in the study and will be based on prednisone equivalent dose.

Prednisone equivalent dose is calculated as [dose of ATC]*[equivalence factor prednisone]/[equivalence factor ATC]. Following [equivalence factors] are used:

- Betamethasone [1.5]
- Cortisone [37.5]
- Deflazacort [15]
- Dexamethasone [1.5]
- Fluocortolone [10]
- Hydrocortisone [30]
- Hydrocortisone sodium phosphate [30]
- Methylprednisolone [8]
- Methylprednisolone acetate [8]
- Methylprednisolone sodium succinate [8]
- Paramethasone [4]
- Prednisolone [10]
- Prednisone [10]
- Prednisolone acetate [10]
- Prednisone acetate [10]
- Prednisolone sodium succinate [10]
- Prednylidene [12]
- Rimexolone [20]
- Triamcinolone [8]

Example: calculation of equivalent dosage of 12 mg methylprednisolone: $12 * 10 / 8 = 15$ mg prednisone.

Following rules will be applied to calculate the daily OCS dose (per body weight):

- Records with (partially) missing dates will be imputed as detailed in section 2.3.2.
- If dates of administration records overlap, the overlapping reported doses will be added together.

	Statistical Analysis Plan	
ARGX-113-2010	Final analysis	Final 1.0 of 29APR2025

- If for a given day, no record exists in the eCRF indicating OCS use that day, the dose will be assumed to be 0 mg.
- If an administration is reported as dose per administration with frequency, then the doses should be allocated to the correct dates, taking the start date and the frequency into account.

Example:

- Dose: 40 mg
- Frequency: every other day
- Start - Stop date: 01JAN2022 - 03JAN2022

This will result in:

- 40 mg be allocated to 01JAN2022
- 0 mg allocated to 02JAN2022
- 40 mg allocated to 03JAN2022
- OCS dose per body weight will be calculated based on the most recent assessment of body weight available for a study day.

3.4.3 *Presentation of results*

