4. EFFICACY, PHARMACODYNAMIC, AND IMMUNOGENICITY ANALYSES

4.1 EFFICACY AND QUALITY OF LIFE

All efficacy endpoints are secondary endpoints in this OLE study and will be evaluated descriptively.

4.1.1 *Available data*

Investigators report the participant's best disease status in episodes with start and end date (no CDA, CDA, CR, PR, Relapse and Treatment failure). Furthermore, BPDAI activity and total score, IGA-BP scores and itch NRS are collected over time.

Quality of life is assessed over time using the ABQOL, DLQI and EQ-5D-5L questionnaires.

The health impact of long-term glucocorticoid use is assessed via the Aggregate Improvement Score (AIS) and Cumulative Worsening Score from the Glucocorticoid Toxicity Index (GTI) and via the GTI Specific List (GTI-SL).

4.1.2 *Derivation rules*

The following endpoints will be derived **for each treatment period separately**:

- 1) Participants achieving CR while off OCS for ≥ 8 weeks (CROff). A participant will be considered a CROff responder if the following criteria are met simultaneously for ≥ 8 weeks (56 days):
 - The participant's reported disease status is CR
 - The participant is off OCS therapy
 - The participant does not receive any rescue therapy (as indicated by the investigator on the eCRF)

Else, the participant will be considered a CROff non-responder. Participants who already have the disease status CR at day 1 of the treatment period or who are off OCS therapy at day 1 of the treatment period or who receive rescue therapy at day 1 of the treatment period, will be considered non-evaluable for this endpoint and will be excluded from this analysis for the corresponding treatment period.

Note: the rules for assessing the OCS dose on a given day are described in section 3.4.2. Similarly, these rules can be used to assess whether rescue therapy is received on a given day. Additionally for rescue therapy, a frequency of PRN (pro re nata, or 'as needed') will be interpreted as a dose of 1 time per week.

- 2) Participants achieving CR or PR while off OCS for ≥ 8 weeks (CR/PROff). A participant will be considered a CR/PROff responder if the following criteria are met simultaneously for ≥ 8 weeks (56 days):
 - The participant's reported disease status is CR or PR (continuously or alternately)
 - The participant is off OCS therapy
 - The participant does not receive any rescue therapy (as indicated by the investigator on the eCRF)

	Statistical Analysis Plan	

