ARGX-113-2010	Final analysis	Final 1.0 of 29APR2025

Else, the participant will be considered a CR/PROff non-responder. Participants who already have the disease status CR or PR at day 1 of the treatment period or who are off OCS therapy at day 1 of the treatment period or who receive rescue therapy at day 1 of the treatment period, will be considered non-evaluable for this endpoint and will be excluded from this analysis for the corresponding treatment period.

- 3) Participants achieving CR while on minimal OCS therapy for ≥ 8 weeks (CRmin). A participant will be considered a CRmin responder if the following criteria are met simultaneously for ≥ 8 weeks (56 days):
- The participant's reported disease status is CR
 - The participant receives ≤ 0.10 mg/kg/day of prednisone (or an equivalent dose of another OCS)
 - The participant does not receive any rescue therapy (as indicated by the investigator on the eCRF). OCS used as rescue therapy will not be considered as rescue therapy if the above criterium of minimal OCS therapy is still met.

Else, the participant will be considered a CRmin non-responder. Participants who already have the disease status CR at day 1 of the treatment period or who are on minimal (≤ 0.10 mg/kg/day) OCS therapy at day 1 of the treatment period or who receive rescue therapy at day 1 of the treatment period, will be considered non-evaluable for this endpoint and will be excluded from this analysis for the corresponding treatment period.

- 4) Participants with treatment failure.

The following endpoints will be derived **for each treatment period separately and additionally for the observation phase:**

- 5) Participants achieving CR while off both OCS and efgartigimod PH20 SC for ≥ 8 weeks (CROff without IMP). A participant will be considered a responder for CROff without IMP if the following criteria are met simultaneously for ≥ 8 weeks (56 days):
- The participant's reported disease status is CR
 - The participant is off OCS therapy
 - The participant is off IMP
 - The participant does not receive any rescue therapy (as indicated by the investigator on the eCRF)

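### Scoring alternate-day OCS as full dose, then 0 mg, lets the tablet day decide day-1 evaluability and blocks CRmin for means above 0.05 and up to 0.10 mg/kg/day

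*SAP*

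**What the plan says.** SAP 3.4.2 states that "OCS dose (mg) and OCS dose per body weight (mg/kg) will be calculated for each day in the study", in prednisone equivalents. For a record given as a dose with a frequency, "then the doses should be allocated to the correct dates, taking the start date and the frequency into account". The worked example is 40 mg every other day over three days: 40 mg on the first, then "0 mg allocated to 02JAN2022" and "40 mg allocated to 03JAN2022". Nothing is averaged over the dosing interval.

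SAP 4.1.2 links the response endpoints to this rule. Its note under CROff says that "the rules for assessing the OCS dose on a given day are described in section 3.4.2", and that the same rules can be used for rescue therapy, with as-needed rescue read as one dose per week. The CRmin dose criterion is "The participant receives ≤ 0.10 mg/kg/day of prednisone (or an equivalent dose of another OCS"), to hold together with CR and absence of rescue for 56 days.

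Day 1 of each treatment period also decides who enters the denominator. Participants "who are off OCS therapy at day 1 of the treatment period" are non-evaluable for CROff and CR/PROff. Those at or below 0.10 mg/kg/day on day 1 are non-evaluable for CRmin. Disease status and rescue use on day 1 are further conditions for all three endpoints.

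Two other parts of the SAP bear on this. Section 3.3.2 defines OCS therapy by record and places therapies in phases by start and stop dates. Section 3.2.2 defines baseline OCS by whether the medication is taken on study day 1.

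**The concern.** The protocol's Definitions of Terms express minimal OCS therapy as a dosage per kilogram per day, which is a rate. The SAP tests it against the amount taken on each calendar day. With less-than-daily dosing these differ: on alternate days the tablet day carries twice the mean and the next day carries nothing.

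Two things are at stake. First, SAP 4.1.3 takes as the denominator the participants who were evaluable at least once, so day-1 status fixes who is counted. If a 0 mg day inside an ongoing course is read as off OCS, two participants on the same regimen can be classified differently because of one calendar day. Where the OCS start date is partly missing, SAP 2.3.2 imputes it, and the imputed date then sets the pattern. Second, a participant in CR whose average intake satisfies the minimal-OCS rate can be denied the CRmin run by the scoring convention alone.

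**Working it through.** **Reproducing the SAP's figures.** Allocating 40 mg every other day over three days gives 40, 0, 40 mg, as stated. Over 56 days the mean is 20 mg/day. The SAP's conversion example also reproduces: 12 × 10 / 8 = 15 mg prednisone.

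**Inputs.** Threshold 0.10 mg/kg/day and run of 56 days (SAP 4.1.2); daily allocation (SAP 3.4.2). Body weights and alternate-day doses are assumptions. A 0 mg day is taken to satisfy the at-or-below criterion, which is its literal wording.

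**CRmin run.** For dose D every other day at weight w:

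- dosing-day score = D / w
- mean = D / (2w)
- every day qualifies only if D / w ≤ 0.10, that is, if the mean is ≤ 0.05

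The longest qualifying run over 112 days (twice 56) of unchanged alternate-day dosing is:

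| Weight (kg) | Dose every other day (mg) | Dosing-day score (mg/kg) | Mean (mg/kg/day) | Longest run (days) |
|---|---|---|---|---|
| 50 | 5 | 0.100 | 0.050 | 112 |
| 50 | 10 | 0.200 | 0.100 | 1 |
| 60 | 7.5 | 0.125 | 0.0625 | 1 |
| 70 | 5 | 0.071 | 0.036 | 112 |
| 70 | 10 | 0.143 | 0.071 | 1 |
| 80 | 7.5 | 0.094 | 0.047 | 112 |
| 80 | 15 | 0.188 | 0.094 | 1 |

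The blocked range is therefore a mean above 0.05 and up to 0.10 mg/kg/day. For comparison, 5 mg every day at 70 kg (the Table 6 minimal dose for that band) is scored 5 / 70 = 0.071 daily and qualifies. The same total taken as 10 mg every other day does not. With the dose averaged over two days, every regimen in the table qualifies on 112 of 112 days.

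**Day 1, OCS condition only:**

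| Endpoint | Day 1 is a tablet day | Day 1 is a 0 mg day |
|---|---|---|
| CROff, CR/PROff, any alternate-day dose | condition met | non-evaluable |
| CRmin, dosing-day dose above 0.10 mg/kg | condition met | non-evaluable |
| CRmin, dosing-day dose 0.10 mg/kg or less | non-evaluable | non-evaluable |

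Take the SAP's own example at an assumed 70 kg. The mean is 20 / 70 = 0.286 mg/kg/day, well above minimal. On a tablet day the score is 40 / 70 = 0.571; on the next day it is 0, and the participant drops out of all three denominators. If day 1 is unrelated to the tablet schedule, the chance of this is 1 in 2.

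**What is not affected.** The CROff and CR/PROff numerators do not change, because an alternate-day course breaks a 56-day off-OCS run under either convention. For rescue, weekly allocation leaves at most 6 free days between doses, so the 56-day rescue-free requirement still works. Only the day-1 rescue exclusion can be missed.

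**The case against.** The strongest reply is that the affected regimen is hypothetical. Protocol Table 6, and Table 9 for China, list daily doses only. A footnote to each tells investigators to keep to the listed levels unless safety could be compromised. The SAP's 40 mg example is a programming illustration, not evidence of use. Steps are held for two weeks or less: in the 70 to <75 kg band the path is 5, 2.5, 0 mg, about four weeks at two weeks per step. Days at 0 mg count toward CRmin, so a participant who tapers can still qualify later. This stands and limits the size. It does not remove the point, because SAP 3.3.2 takes in oral glucocorticoids from any eCRF page and 3.4.2 provides for alternate-day records.

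A second reply is that SAP 3.3.2 defines OCS therapy by record, so an ongoing course might already count as on OCS on its 0 mg days. That reading is possible, but the SAP does not state it, and the note in 4.1.2 points to the daily dose. Two programmers could differ.

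Third, scoring the amount taken each day is a conservative reading of a ceiling, and unrestricted averaging has its own fault. At 70 kg, 40 mg once weekly gives 40 / 7 / 70 = 0.082 mg/kg/day and would pass as minimal despite a dosing-day amount of 0.571 mg/kg. This is correct and limits the fix.

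A reader might infer that nobody on alternate-day OCS averaging 0.10 mg/kg/day or less can ever reach CRmin. The documents do not support that: at means of 0.05 or less every day qualifies, and above that the block lasts only as long as the regimen. It would be true only if a 0 mg day failed the criterion, and the SAP does not say so.

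**Conclusion.** The point holds in a limited form. Applied literally, the rule makes the day-1 OCS condition depend on the tablet day. For CROff and CR/PROff this applies at any alternate-day dose; for CRmin it applies when the dosing-day dose exceeds 0.10 mg/kg. The other day-1 conditions still have to be met. The rule also prevents the CRmin run for alternate-day means above 0.05 and up to 0.10 mg/kg/day while that regimen continues.

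The effect on results is probably small. The number of participants on less-than-daily OCS is not given and could be zero. The endpoints are secondary and descriptive with no hypothesis test, and OCS records and derived responses are listed per participant, so cases would be visible. The conclusion rests on reading a 0 mg day as off OCS and as satisfying the CRmin ceiling. It is still worth correcting, because the rule as written gives a wrong classification for the SAP's own example.

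**What to change.** Change the analysis rule only, in SAP 3.4.2 and 4.1.2:

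1. Every day from the start to the stop date of an ongoing less-than-daily OCS record counts as on OCS. An ongoing rescue record, including as-needed use, likewise counts as rescue on day 1.
2. For the CRmin threshold, the CRmin day-1 exclusion and the baseline OCS dose, an alternate-day record contributes its dose divided by 2 on each day (40 mg every other day = 20 mg/day).
3. Do not average over longer intervals such as weekly dosing. Keep date allocation for listings.

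The cost is a small programming change and a convention that must be footnoted in the affected tables; no new data are needed. One limit remains: for intervals longer than two days, the CRmin day-1 exclusion still uses the date-allocated dose.

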4. EFFICACY, PHARMACODYNAMIC, AND IMMUNOGENICITY ANALYSES

4.1 EFFICACY AND QUALITY OF LIFE

All efficacy endpoints are secondary endpoints in this OLE study and will be evaluated descriptively.

4.1.1 *Available data*

Investigators report the participant's best disease status in episodes with start and end date (no CDA, CDA, CR, PR, Relapse and Treatment failure). Furthermore, BPDAI activity and total score, IGA-BP scores and itch NRS are collected over time.

Quality of life is assessed over time using the ABQOL, DLQI and EQ-5D-5L questionnaires.

The health impact of long-term glucocorticoid use is assessed via the Aggregate Improvement Score (AIS) and Cumulative Worsening Score from the Glucocorticoid Toxicity Index (GTI) and via the GTI Specific List (GTI-SL).

4.1.2 *Derivation rules*

The following endpoints will be derived **for each treatment period separately**:

- 1) Participants achieving CR while off OCS for ≥ 8 weeks (CROff). A participant will be considered a CROff responder if the following criteria are met simultaneously for ≥ 8 weeks (56 days):
 - The participant's reported disease status is CR
 - The participant is off OCS therapy
 - The participant does not receive any rescue therapy (as indicated by the investigator on the eCRF)

Else, the participant will be considered a CROff non-responder. Participants who already have the disease status CR at day 1 of the treatment period or who are off OCS therapy at day 1 of the treatment period or who receive rescue therapy at day 1 of the treatment period, will be considered non-evaluable for this endpoint and will be excluded from this analysis for the corresponding treatment period.

Note: the rules for assessing the OCS dose on a given day are described in section 3.4.2. Similarly, these rules can be used to assess whether rescue therapy is received on a given day. Additionally for rescue therapy, a frequency of PRN (pro re nata, or 'as needed') will be interpreted as a dose of 1 time per week.

- 2) Participants achieving CR or PR while off OCS for ≥ 8 weeks (CR/PROff). A participant will be considered a CR/PROff responder if the following criteria are met simultaneously for ≥ 8 weeks (56 days):
 - The participant's reported disease status is CR or PR (continuously or alternately)
 - The participant is off OCS therapy
 - The participant does not receive any rescue therapy (as indicated by the investigator on the eCRF)

	Statistical Analysis Plan	
ARGX-113-2010	Final analysis	Final 1.0 of 29APR2025

Else, the participant will be considered a CR/PROff non-responder. Participants who already have the disease status CR or PR at day 1 of the treatment period or who are off OCS therapy at day 1 of the treatment period or who receive rescue therapy at day 1 of the treatment period, will be considered non-evaluable for this endpoint and will be excluded from this analysis for the corresponding treatment period.

- 3) Participants achieving CR while on minimal OCS therapy for ≥ 8 weeks (CRmin). A participant will be considered a CRmin responder if the following criteria are met simultaneously for ≥ 8 weeks (56 days):
- The participant's reported disease status is CR
 - The participant receives ≤ 0.10 mg/kg/day of prednisone (or an equivalent dose of another OCS)
 - The participant does not receive any rescue therapy (as indicated by the investigator on the eCRF). OCS used as rescue therapy will not be considered as rescue therapy if the above criterium of minimal OCS therapy is still met.

Else, the participant will be considered a CRmin non-responder. Participants who already have the disease status CR at day 1 of the treatment period or who are on minimal (≤ 0.10 mg/kg/day) OCS therapy at day 1 of the treatment period or who receive rescue therapy at day 1 of the treatment period, will be considered non-evaluable for this endpoint and will be excluded from this analysis for the corresponding treatment period.

- 4) Participants with treatment failure.

The following endpoints will be derived **for each treatment period separately and additionally for the observation phase:**

- 5) Participants achieving CR while off both OCS and efgartigimod PH20 SC for ≥ 8 weeks (CROff without IMP). A participant will be considered a responder for CROff without IMP if the following criteria are met simultaneously for ≥ 8 weeks (56 days):
- The participant's reported disease status is CR
 - The participant is off OCS therapy
 - The participant is off IMP
 - The participant does not receive any rescue therapy (as indicated by the investigator on the eCRF)

Else, the participant will be considered a non-responder for CROff without IMP. Participants who enter the ARGX-113-2010 study under protocol version 3 (26 April 2024) or 4 (02 May 2024) will be considered non-evaluable for this endpoint. Furthermore, participants who were randomized to the placebo arm in the ARGX-113-2009 study and who enter the ARGX-113-2010 study in the observation phase, will be considered non-evaluable for this endpoint in the observation phase.

- 6) Participants achieving CR or PR while off both OCS and efgartigimod PH20 SC for ≥ 8 weeks (CR/PROff without IMP). A participant will be considered a

	Statistical Analysis Plan	
ARGX-113-2010	Final analysis	Final 1.0 of 29APR2025

responder for CR/PROff without IMP if the following criteria are met simultaneously for ≥ 8 weeks (56 days):

- The participant's reported disease status is CR or PR (continuously or alternately)
- The participant is off OCS therapy
- The participant is off IMP
- The participant does not receive any rescue therapy (as indicated by the investigator on the eCRF)

Else, the participant will be considered a non-responder for CR/PROff without IMP. A participant will be considered non-evaluable for this endpoint using the same rules as for CROff without IMP.

- 7) Duration of sustained remission will be calculated for participants achieving CR while off both OCS and efgartigimod PH20 SC for ≥ 8 weeks (i.e., responders for CROff without IMP) within a treatment period.
 - Start date of sustained remission is 1 week (7 days) after the last IMP administration in the treatment period
 - End date of sustained remission is:
 - the start date of first relapse after achieving CROff without IMP
 - the start date of a (next) treatment period
 - the start date of OCS therapy after achieving CROff without IMP
 - the start date of a rescue therapy after achieving CROff without IMP
 whichever comes first. If none of the above occurs, the participant will be censored at the end date of the study (end date of last phase).
 - Duration of sustained remission (in days) = end date - start date + 1
- 8) Relapse will be evaluated for participants having or achieving CDA, CR or PR during the treatment period (or observation phase). The evaluation period for relapse is till the end of the treatment period (or observation phase) in case a (next) treatment period starts, or else till the end of the study. Only the first relapse in a treatment period (or observation phase) will be considered.
- 9) Time to relapse:
 - Start date is the first day with status CDA, CR or PR in the treatment period (or observation phase)
 - End date is:
 - the start date of first relapse after having or achieving CDA, CR or PR
 - the end date of the study (end date of last phase), if no relapse
 - Time to relapse (in days) = end date - start date + 1
- 10) For participants with relapse, severity of (first) relapse will be calculated as the BPDAl total score at the onset of relapse (use the first available nonmissing BPDAl total score in the interval of relapse) minus the BPDAl total score at the preceding visit (use the most recent preceding visit for which a nonmissing BPDAl total score is available). Severity of relapse will be categorized as <0 , $0- <10$, $10- <20$, $20- <30$, or >30 .

	Statistical Analysis Plan	
ARGX-113-2010	Final analysis	Final 1.0 of 29APR2025

The following endpoints will be derived **overall**:

- 11) Changes and percent changes from study baseline will be calculated for BPDAI activity and total score.
- 12) Changes from study baseline will be calculated for itch NRS 24-hour average and worst scores.
- 13) C-GTI: Composite Glucocorticoid Toxicity Index comprises the Aggregate Improvement Score (AIS) and the Cumulative Worsening Score (CWS). Details of AIS and CWS derivations are specified in appendix 9.1.
- 14) A total ABQOL score is calculated as the sum of all 17 items score 0 to 3 with higher score indicating worse condition. Missing items are imputed with the average score of the present items if at least half (9) of the items are present. The total score is rounded to the highest integer.
- 15) Changes from study baseline will be calculated for EQ-5D-5L VAS score, DLQI score and total ABQOL score.

4.1.3 *Presentation of results*

Efficacy results will be presented for the ROL analysis set, unless mentioned otherwise. For tables by analysis visit, only the study baseline and last assessment analysis visits will be shown. Other analysis visits will be included in listings.

A frequency tabulation will be created for the number and percentage of participants who achieved CROff at least once during the study (i.e., in any treatment period). The table will also present the number of participants who are evaluable for the endpoint at least once during the study. This number will serve as denominator for the percentage calculation. This table will be based on the SAF analysis set.

Similar frequency tabulations will be created for the number and percentage of participants who achieved:

- CR/PROff
- CRmin
- Treatment failure

Similar frequency tabulations, based on the ROL analysis set, will be created for:

- CROff without IMP
- CR/PROff without IMP
- Relapse

Duration of sustained remission and time to relapse will be descriptively presented with median times, quantiles and number and percentage of censored observations and observations with event. Only the participant's first evaluation during the study will be included as observation.

Duration of sustained remission will be presented for the SAF analysis set.

A frequency tabulation will be created for categorized severity of relapse, for the participant's first relapse during the study.

	Statistical Analysis Plan	
ARGX-113-2010	Final analysis	Final 1.0 of 29APR2025

Descriptive statistics will present the actual values, changes and percent changes from study baseline of the BPDAl activity and total scores per analysis visit (baseline and last assessment).

Frequency tabulations will be provided for the outcome of IGA-BP per analysis visit (baseline and last assessment). Additionally, cumulative percentages (starting with the best outcome result) will be calculated.

Descriptive statistics will present the actual values and changes from study baseline of the itch NRS 24-hour average and worst scores per analysis visit (baseline and last assessment).

Descriptive statistics will be provided for the C-GTI scores AIS and CWS at the last assessment.

Frequency tabulations will be provided for the outcomes of the ABQOL (17 items), EQ-5D-5L (5 dimensions) and DLQI (10 items), similar to the frequency tabulations of the IGA-BP outcomes. Descriptive statistics on absolute values and changes from study baseline for EQ-5D-5L VAS score, DLQI score and Total ABQOL score will be calculated per analysis visit (baseline and last assessment), similar to the descriptive statistics of the itch NRS scores.

Listings will be created for:

- Disease status, including the derived response variables (CROff, CR/PROff, CRmin, etc.)
- Duration of sustained remission and time to relapse, including the reason for censoring (if applicable) and the severity of relapse
- Lesion assessments
- BPDAl assessments
- IGA-BP assessments
- Itch NRS assessment
- Calculated C-GTI scores and complementary GTI specific list (GTI-SL)
- ABQOL, EQ-5D-5L and DLQI data

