3.2 DEMOGRAPHIC AND OTHER BASELINE CHARACTERISTICS

3.2.1 *Available data*

The following parameters will be available:

- Demographics: sex at study start, childbearing potential, year of birth, age at informed consent, race, ethnicity, height, body weight and BMI at study baseline, date of signing ICF
- Baseline disease characteristics: disease status at study baseline (no CDA, CDA, CR, PR, Relapse, Treatment failure), BPDAl activity and total score at study baseline, IGA-BP at study baseline, itch NRS 24-hour average and worst score at study baseline

	Statistical Analysis Plan	
ARGX-113-2010	Final analysis	Final 1.0 of 29APR2025

- Study entry status: date of protocol version at entry, participant receiving rescue therapy at study baseline (yes, no), type of rescue therapy at study baseline (ATC class level 3), participant receiving OCS at study baseline (yes, no), and if yes, OCS dose at study baseline (mg) and OCS dose per body weight at study baseline (mg/kg)

3.2.2 *Derivation rules*

The following parameters will be derived:

- Age at informed consent, categorized (18 - <65, 65 - <75, 75 - <85, >=85)
- Height: if height is not available in the database of ARGX-113-2010, the height at screening of ARGX-113-2009 will be taken.
- BMI at study baseline (kg/m²) = (body weight (kg) at study baseline) / (height (m))².
- BMI at study baseline, categorized (Underweight: < 18.5 kg/m², Normal weight: 18.5 -< 25 kg/m², Overweight: 25 -< 30 kg/m², Obese: >= 30 kg/m²)
- Race, categorized (Asian, Black or African American, White, Other)
- Geographical region: Asia (Japan, China), North America (US, Canada), EU region+UK (EU/EEA/EFTA/UK), Rest of world
- BPDAl activity score at study baseline, categorized: <20, 20-56, >56
- OCS at study baseline: any use of systemic OCS on study day 1, i.e.. any record from any eCRF page with medication class = 'GLUCOCORTICOIDs' and route = 'ORAL' for which the available information indicates that the medication is taken on study day 1.
- Rescue therapy at study baseline: any use of therapy that is indicated as rescue therapy by the investigator on the eCRF page and for which the available information indicates that the medication is taken on study day 1.

3.2.3 *Presentation of results*

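### CRoff and CR/PRoff drop every treatment period begun off OCS, even outside remission, so no planned table gives the remission proportion for OCS-free starts

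*SAP*

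**What the plan says.** **Evaluability (SAP 4.1.2, items 1-3).** Three on-treatment remission proportions are derived for each treatment period. Each has a list of day-1 conditions that make a participant non-evaluable for that period.
- CRoff: "Participants who already have the disease status CR at day 1 of the treatment period or who are off OCS therapy" on that day.
- CR/PRoff: "Participants who already have the disease status CR or PR at day 1 of the treatment period or who are off OCS therapy" on that day.
- CRmin: "Participants who already have the disease status CR at day 1 of the treatment period or who are on minimal" OCS, that is, at most 0.10 mg/kg/day.

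In all three the last alternative is rescue therapy on day 1. The conditions are joined by *or*.

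**Denominator (SAP 4.1.3).** The tables count participants evaluable at least once in the study: "This number will serve as denominator for the percentage calculation".

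**Zero dose.** SAP 3.4.2 covers days without a record: if "no record exists in the eCRF indicating OCS use that day, the dose will be assumed to be 0 mg". Protocol Table 6 has separate rows for off OCS and for minimal OCS. The SAP does not say whether 0 mg meets the CRmin threshold.

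**Protocol.** For these three proportions, Table 4 adds one restriction by footnote: the participant must be off rescue therapy. The CRoff entry in the SAP's Definition of Terms has no day-1 OCS condition. Section 2.3.2 allows efgartigimod alone. Section 6.3 favours starting it without OCS where the investigator judges that disease status permits. The rationale for amendment 2 includes learning about efficacy without concurrent OCS.

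**The concern.** A participant with active disease who starts efgartigimod without OCS has not met CRoff or CR/PRoff on day 1, because both need remission and freedom from OCS together for 56 days. The SAP still counts that participant as neither responder nor non-responder for the period. The two proportions therefore describe only treatment periods that began on OCS, while the current protocol favours the other kind of start where possible and amendment 2 set out to study it.

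Only day 1 matters. Protocol 6.3 foresees adding OCS later if there is no improvement. Someone who does so, tapers off and then holds CR for 8 weeks is still excluded. The same applies to a participant on no BP therapy who relapses and must then start efgartigimod (protocol 6.3.2, situation 3A), unless OCS is running by day 1.

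At stake is what two secondary proportions mean, and whether the study reports remission after an OCS-free start.

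**Working it through.** The documents state no sample size, expected rate or day-1 OCS split for these endpoints, so there is no figure to reproduce. The check has three steps.

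**1. Apply the rules to a grid.** Take day-1 OCS at three levels (0; above 0 to 0.10; above 0.10 mg/kg/day) and status at three levels (neither CR nor PR; PR; CR), with no rescue therapy: 3 x 3 = 9 states. The last column applies the change set out under the fix.

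| Endpoint | Evaluable now | After the fix |
|---|---|---|
| CRoff | OCS above 0 and not CR: 2 x 2 = 4 | not CR: 3 x 2 = 6 |
| CR/PRoff | OCS above 0 and neither CR nor PR: 2 x 1 = 2 | neither: 3 x 1 = 3 |
| CRmin, 0 mg counted as minimal | above 0.10 and not CR: 1 x 2 = 2 | add 0 mg, not CR: 2 + 2 = 4 |
| CRmin, 0 mg not counted as minimal | 0 or above 0.10, and not CR: 2 x 2 = 4 | unchanged: 4 |

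The regained states all have 0 mg on day 1. For CRoff they are neither and PR; for CR/PRoff, neither; for CRmin on the first reading, neither and PR. None is already in the status that its endpoint targets. These are rule states, not participants.

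**2. Follow one participant.** Take an entrant under protocol v3.0 or v4.0 with one treatment period who on day 1 is off OCS, in neither CR nor PR, and not on rescue.
- CRoff: non-evaluable.
- CR/PRoff: non-evaluable.
- CRmin: non-evaluable if 0 mg is minimal OCS, otherwise evaluable.

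That is 0 of 3 on-treatment proportions (1 of 3 on the other reading); after the fix, 3 of 3. The two off-drug proportions cannot fill the gap, since for them "Participants who enter the ARGX-113-2010 study under protocol version 3 (26 April 2024) or 4 (02 May 2024) will be considered non-evaluable". That closure follows protocol Table 4, footnote b, and has nothing to do with OCS, so it is left out of the count.

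**3. Illustrate the possible size (all values assumed).** Let f be the share of the enlarged evaluable set that is off OCS on day 1, with one treatment period per participant, and r_on and r_off the response rates.
- Reported now: r_on.
- After the fix: (1 - f) x r_on + f x r_off.
- Shift: f x (r_off - r_on).

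With equal rates the shift is 0. With a 30-point difference it is 0.1 x 30 = 3 points, 0.3 x 30 = 9 points or 0.5 x 30 = 15 points, and its sign follows the difference. So for f from 10% to 50% and differences from -30 to +30 points, the movement is 0 to 15 points in either direction.

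Example: 100 starts, f = 40%, r_on = 40%. The SAP reports 24/60 = 40.0% whatever happens to the other 40 participants. Counting them gives (24 + 8)/100 = 32.0% if r_off is 20%, 40.0% if it is 40%, and (24 + 28)/100 = 52.0% if it is 70%.

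The formula does not carry over to a participant with two periods. One already evaluable through an on-OCS period is not added to the denominator, but can change from non-responder to responder.

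**The case against.** **It is a legitimate analysis choice.** Protocol section 9 leaves technical detail to the SAP. The day-1 remission exclusion is also absent from the protocol endpoint, and it is not challenged here. All the exclusions could be read as removing people who already meet part of the endpoint or are on rescue, and coming off OCS fits the protocol's aim of lower OCS exposure. This stands as an argument for keeping the on-OCS set as a labelled analysis. It does not justify that set as the only one: a participant outside the target remission has not met the joint endpoint, and the day-1 remission exclusion already prevents carried-over credit.

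**The group may be small.** Day 1 of the first treatment period is often not a new start, because participants from the parent study's efgartigimod arm continue weekly dosing, and those on OCS there continue their taper. This stands. A reader might infer that most participants are lost or that the proportions are inflated; the documents give no split and support neither inference.

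**Much is reported anyway.** The evaluable number is printed. A listing will show "Disease status, including the derived response variables", and OCS administration is listed too. The BPDAI, IGA-BP, itch and relapse tables carry no OCS exclusion. So it would be wrong to infer that OCS-free starters vanish from the efficacy results. What is missing is narrower: no table gives their proportion reaching 8 weeks of remission off OCS on treatment.

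**Conclusion.** The point holds for CRoff and CR/PRoff and should be fixed. Being off OCS on day 1 alone removes the period from both, for participants who have not met the endpoint. For CRmin the same effect is conditional on 0 mg counting as minimal OCS; it should not be read as certain.

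The exclusion applies per treatment period, so a participant can still count through another period that began on OCS. The number affected and the direction are unknown; the range of 0 to 15 points rests wholly on the assumed shares and differences and on one period per participant. All efficacy endpoints are secondary and descriptive with no hypothesis test, so this changes the population that the proportions describe and affects no error rate or power.

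**What to change.** - In items 1 and 2, delete only the condition of being off OCS on day 1. Keep the day-1 remission and rescue exclusions as written.
- Report each proportion overall and by day-1 OCS use (off, on), with the number non-evaluable by reason. For participants with two periods, either classify by the first evaluable period or tabulate by treatment period, and say which.
- Keep the present on-OCS-at-day-1 set as a supportive analysis, labelled as such.
- For CRmin, state whether 0 mg counts as minimal OCS, both in the day-1 rule and in the response criterion. If it does, do not exclude 0 mg starts that are not in CR.

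The cost is SAP wording, a revised evaluability flag per endpoint and an added table. No new data are needed: daily OCS dose, rescue use and disease status are already available to the derivations. The downside is that the overall proportion mixes OCS-free and on-OCS starts, which the split makes visible.
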